# • Clinical chemistry:

- Metabolism: glucose, total protein, albumin, creatine phosphokinase.
- Electrolytes: sodium, potassium, chloride, calcium, phosphorus, bicarbonate.
- Renal function: creatinine, eGFR, blood urea nitrogen, uric acid.
- Liver function (also measured at Week 4, and Week 12, except GGT and LDH): alanine aminotransferase (ALT), aspartate aminotransferase (AST), alkaline phosphatase (ALP), gamma glutamyl transferase (GGT), total bilirubin, and in case of total bilirubin values above the normal range, must include direct and indirect bilirubin, lactate dehydrogenase (LDH).

Technical formulas are described in Section 2.5.1.

# 2.1.4.4 Vital signs variables

Vital Signs parameters include Weight, Heart Rate (HR), Systolic and Diastolic Blood Pressure ([SBP] and [DBP]) in sitting position.

# 2.1.4.5 Electrocardiogram variables

Not applicable

#### 2.1.5 Other variables

Other assessment variables listed below are defined using same definitions and rules as for calculated LDL-C, when applicable (see Section 2.1.3).

- The proportion of patients with two consecutive (spaced out by at least 21 days) calculated LDL-C <25 mg/dL (<0.65 mmol/L) (respectively two consecutive calculated LDL-C <15 mg/dL,i.e. < 0.39 mmol/L) during the OLE treatment period.
- For the patients with two consecutive results as described above, the time from the first study treatment administration in OLE study to the first calculated LDL-C<25 mg/dL (respectively, calculated LDL-C <15 mg/dL for these patients).

#### 2.1.6 Anti-alirocumab antibodies variables

Anti-alirocumab antibodies (ADA) are assessed at Week 0 (before the IMP injection in OLE study), Week 24, Week 48, Week 72, Week 96, Week 120, Week 144 and Week 168)/or early termination .

ADA measurements will be assigned to similar analysis windows as defined for efficacy parameters (Table 1).

• The following variables will be described: ADA response (Positive or Negative).

For ADA positive:

- Titer levels
- Neutralizing status (Positive or Negative)
- Pre-existing positive ADA defined as patients with positive ADA response at baseline of the parent study with less than 4-fold increase in titer during the OLE period
- Treatment-emergent ADA positive response during the OLE period, defined as:
  - Patients with no positive ADA response at baseline of the parent study but with a positive response ADA response during the OLE period; OR
  - Patients with positive ADA response at baseline of the parent study and at least 4-fold increase in ADA titer during the OLE period.

Treatment-emergent ADA positive responses during the OLE period will be described according to the ADA status during the double-blind period (Pre-existing, Negative and Treatment-emergent ADA status).

For treatment emergent positive ADA during the OLE period, the following categories for ADA duration will be applied:

- A persistent positive response is a treatment-emergent ADA positive response detected in at least 2 consecutive samples post first OLE injection separated by at least a 12-week period
- An indeterminate duration positive response is defined as ADA present only at the last sampling time point in OLE period
- A transient positive response is defined as any treatment-emergent positive ADA response that is neither considered persistent nor indeterminate

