10.1.1.5 Visit 5/ Week 24 (Day 169 ± 7)

- Collect adverse events
- Record concomitant medication
- Take vital signs including heart rate and blood pressure
- Get body weight measurement
- Physical examination
- Data collection on IMP administration and IMP compliance check by review of diary and treatment kit
- Obtain fasting blood sample for:
 - Lipids: measure or calculation of total-C, LDL-C, HDL-C, TG, non-HDL-C
 - Hematology
 - Chemistry
 - CPK
 - Liver panel
 - Anti-alirocumab antibodies
 - -
- Local urine pregnancy test (females of childbearing potential only).

- Completion of EQ-5D questionnaire by patient
- IVRS/IWRS contact for allocation of a batch number for treatment kit
- IMP kit dispensation and treatment administration package should be provided. The patient injection instruction manual and diary may be given, as needed.
- Reminders
 - An appointment will be given for the next visit.
 - Patient to bring the diary and used kits and unused auto-injectors at the next visit.

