10.1.1.17 End-of-treatment visit: Visit 17/ Week 168/ Month 40 (Day 1177± 7)

The end of study is scheduled to be in second quarter 2017 or when the drug will become commercially available for the patient in the respective country whatever comes first. Thus, the End-of-treatment visit might be performed earlier than on Week 168 according to the date of inclusion of each patient in the OLE study, or if the patient early discontinues the study.

- Collect adverse events
- Record concomitant medication
- Take vital signs including heart rate and blood pressure
- Get body weight measurement
- Physical examination
- Review patient's diet. Patient should be on a NCEP-ATPIII TLC diet or equivalent.
- Data collection on IMP administration and IMP compliance check by review of diary and treatment kit
- IVRS/IWRS contact to document the end of treatment
- Obtain fasting blood sample for:
 - Lipids: measure and/or calculation of total-C, LDL-C, HDL-C, TG, non-HDL-C, Apo B, Apo A-1, ratio Apo B/Apo A-1, and Lp (a)

- Hematology
- Chemistry
- CPK
- Liver panel
- Anti-alirocumab antibodies

- Local urine pregnancy test (females of childbearing potential only).
- Completion of EQ-5D questionnaire by patient.
- Reminders
 - For all the patients, those who prematurely discontinue the treatment irrespective of the reason and those who will complete the study, an appointment will be given for the Follow up call. This phone call will have to be scheduled 10 weeks after last injection (+/- 7 days).

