# 2.4.7 Analyses of anti-alirocumab antibodies variables

The following summaries will be performed on the ADA population, overall as well as according to treatment received in the parent study (placebo versus alirocumab (regardless of dose)), taking into account all samples collected during the current study regardless of timing in relation to injections:

- ADA results (negative or positive) by time point;
- Neutralizing status (negative or positive) by time point for positive ADA;
- ADA titers using descriptive statistics (median, minimum and maximum) for positive ADA by time point;
- Number (%) of patients with treatment-emergent ADA positive response during the OLE period, overall and according to ADA status during the double-blind period (Pre-existing ADA, Negative ADA status and Treatment emergent ADA status)
- Number (%) of patients with persistent/transient/indeterminate treatment-emergent ADA positive response, overall and according to ADA status during the double-blind period (Pre-existing ADA, Negative ADA status and Treatment emergent ADA status)
- Time to onset of treatment-emergent ADA positive response during the OLE period using descriptive statistics.

Correlations between ADA parameters (eg, titers, treatment-emergent ADA positive status, neutralizing status) and safety and/or efficacy endpoints will be also explored (eg, scatter plot).

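### The SAP's residual definition of a transient ADA response can take in patients who are still antibody-positive at their last OLE sample, inflating transient and deflating indeterminate

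*SAP*

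**What the plan says.** Long-term immunogenicity is a secondary objective (SAP 1.2.2, Protocol 5.2). SAP 2.1.6 defines three duration classes for treatment-emergent ADA responses in the OLE:

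- **Persistent:** a response "detected in at least 2 consecutive samples post first OLE injection separated by at least a 12-week period".
- **Indeterminate:** "An indeterminate duration positive response is defined as ADA present only at the last sampling time point in OLE period".
- **Transient:** "A transient positive response is defined as any treatment-emergent positive ADA response that is neither considered persistent nor indeterminate".

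SAP 2.4.7 commits to a table of these classes: "Number (%) of patients with persistent/transient/indeterminate treatment-emergent ADA positive response". The protocol does not define them, so SAP 2.1.6 is the only rule.

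Sampling after Week 0 is at "Week 24, Week 48, Week 72, Week 96, Week 120, Week 144 and Week 168)/or early termination". The last sample need not fall on the 24-week grid. Protocol 10.1.1.17 says "the End-of-treatment visit might be performed earlier than on Week 168 according to the date of inclusion of each patient in the OLE study". Protocol 6.2.1 ends participation at commercial availability in the patient's country, and Protocol 10.3.4 places the visit within 5 days of early discontinuation where possible. Protocol 10.6.2.1 adds unscheduled ADA samples for allergic events with skin involvement. No ADA sample is scheduled after end of treatment (EOT); the follow-up contact is a phone call.

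The SAP describes the data used in two ways. Section 2.1.6 assigns ADA measurements to windows like those in Table 1. Section 2.4.7 takes all samples collected in the study, whatever their timing relative to injections.

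**The concern.** A single positive at the last sample is called indeterminate because nobody can know how long it would have lasted. The same ignorance applies to any non-persistent response that is positive at the last sample. Under the SAP wording, though, one further positive sample elsewhere in the OLE removes the patient from indeterminate, and unless the 12-week condition is met the label becomes transient. A second positive six weeks after the first is extra evidence of continuing antibody, yet on the all-samples reading it moves the label towards short-lived.

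The error runs one way. Every indeterminate patient is positive at the last sample, so no response that ended negative can land there by mistake. A reader of the duration table would take some unresolved responses for short-lived ones.

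**Working it through.** The documents state no figure for this point, so the check applies the three definitions literally.

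**Inputs.** Protocol visit days for ADA samples: 169, 337, 505, 673, 841 and 1009 (Weeks 24 to 144), plus one EOT sample. Persistence threshold: 12 weeks = 84 days. Visit tolerance ±7 days ("Visit 5/ Week 24 (Day 169 ± 7"), so two scheduled ADA samples are at least (168 − 14)/7 = 22 weeks apart. Windows: SAP Table 1.

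**Step 1: cases, all samples counted, actual dates**

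| Pattern | Days | Class |
|---|---|---|
| First positive Week 48, positive at EOT 3, 7 or 11 weeks later | 337, then 358, 386 or 414 | transient |
| First positive Week 48, positive at EOT 12, 13 or 18 weeks later | 337, then 421, 428 or 463 | persistent |
| Positive at the last two scheduled samples, any EOT date | at least 22 weeks apart | persistent |
| Positive only at EOT | last sample only | indeterminate |
| Week 24 positive, Week 48 negative, Week 72 positive and last | 169, 337, 505 | transient |
| Weeks 24 and 48 positive, Week 72 negative, Week 96 positive and last | 169, 337, 505, 673 | persistent (337 − 169 = 168 ≥ 84) |

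The first row is mechanism (a). The fifth is mechanism (b); its samples sit on the planned visit days, so windowing changes nothing.

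**Step 2: size of (a), all samples counted.** Take a patient first positive on Day 337 and still positive at EOT on one of Days 338 to 505 (168 days). The gap is under 84 days on Days 338 to 420, which is 83 days: 83/168 = 49%.

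**Step 3: size of (a), all Table 1 windows applied, same patient, actual dates within windows**

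- Days 338–357 fall in the Week 48 window, where the Day 337 sample is on target and is kept: 20 days, indeterminate.
- Days 358–399 and 442–483 fall in no window: 42 + 42 = 84 days, indeterminate.
- Days 400–420 fall in the Week 60 window with a gap under 84 days: 21 days, transient.
- Days 421–441 and 484–505: 21 + 22 = 43 days, persistent.

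Total 20 + 84 + 21 + 43 = 168; transient 21/168 = 12.5%. This figure belongs to the Week 48 example, because window widths differ (28 days at Week 36, 42 at Week 60, 56 at Week 108).

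**Step 4: size of (a), only windows at planned ADA visits.** The smallest gap between adjacent windows is Week 120 to Week 144: 980 − 868 = 112 days. This exceeds 84, so (a) cannot occur.

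**Step 5: share of all still-positive patients under (a), all samples counted.** Assume that antibody persists once it appears, that first positivity is equally likely at each of k scheduled samples and EOT, and that k ≥ 1. With an EOT gap under 12 weeks the share is 1/(k + 1): 50%, 33%, 25% and 14% for k = 1, 2, 3 and 6. With a uniform 0 to 24 week gap, multiply by 83/168: 25%, 17%, 12% and 7%.

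**The case against.** The strongest objection is windowing. SAP 2.1.6 assigns ADA measurements to windows, and the phrase in 2.4.7 about all samples concerns timing relative to dosing, so it does not clearly override that. A patient positive at Week 96 and at an EOT visit in Week 102 (about 102 × 7 + 1 = Day 715) falls between the Week 96 window (to Day 693) and the Week 108 window (from Day 729). On windowed data that patient is positive only at the last time point and is indeterminate, as one would want. This stands: mechanism (a) depends on a choice the SAP leaves open. Mechanism (b) does not.

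A second objection is that transient is openly a remainder and makes no claim that antibody cleared, and that in pattern (b) a negative sample did follow the first positive, so the label is a convention. That is fair as far as it goes. But the word suggests a short-lived response, and the SAP already declines to use it for a lone positive at the last sample.

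Third, the table is one of six listed ADA summaries, in a descriptive, uncontrolled study, and status by time point remains available. This limits the consequence.

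Stronger readings are tempting but unsupported:

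- A reader might infer that any off-schedule end of treatment produces the wrong label. Rows 2 to 4 of the table show otherwise, and row 5 shows that an off-schedule end is not needed.
- A reader might infer that the persistent share is wrong. By the SAP's own 12-week criterion it is not; patients move only between transient and indeterminate.
- A reader might infer that every on-and-off responder who ends positive is mislabelled. The last row of the table is a counterexample.
- A reader might infer that affected patients are common. The documents give no distribution of EOT dates.

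**Conclusion.** The concern holds in limited form. SAP 2.1.6 can label a non-persistent response transient although the patient is positive at the last OLE sample, and nothing elsewhere in either document corrects this. The duration table then overstates transient and understates indeterminate. The persistent count, ADA status and neutralizing status by time point, titers, treatment-emergent incidence and time to onset are unaffected.

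For mechanism (a), 49% of possible EOT days are affected if all samples count, 12.5% in the Week 48 example under all Table 1 windows, and none under ADA-visit windows only. These shares apply to patients first positive at the last scheduled ADA visit and still positive at EOT, with EOT equally likely on each day of the 24-week interval. As a share of all still-positive patients the illustrative range is 7% to 25% (all samples, uniform gap, the assumptions of Step 5). Mechanism (b) exists on every reading, but its frequency is unknown. The number of patients cannot be derived, because the documents give neither an ADA rate nor EOT dates.

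**What to change.** In SAP 2.1.6:

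- Indeterminate: *treatment-emergent ADA positive at the last available OLE sample and not meeting the persistent definition.*
- Transient: *treatment-emergent ADA positive, not persistent, with the last available OLE sample negative.*
- Persistent: unchanged.
- Add that the duration rule uses all collected OLE samples with their actual dates, not windowed time points.

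With these definitions no patient positive at the last sample can be transient.

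Cost: two redefined categories, one added sentence and one derivation to reprogram, with no new data. The transient count becomes smaller and the indeterminate count larger.

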#### 2.1.7 Pharmacokinetic variables

Not applicable.

#### 2.1.8 Pharmacodynamic/genomics endpoints

Not applicable.

#### 2.1.9 Quality-of-life endpoints

EQ-5D is a standardized and generic instrument for measuring the health status and health related quality of life for clinical and economic assessment (1). EQ-5D instrument includes 5 items corresponding to the following dimensions: mobility, self-care, usual activities, pain/discomfort, anxiety/depression (Appendix B). Each item can take one of three responses: (1.) "no problem", (2.) "some problems", and (3.) "severe problems".

Response from individual items will be converted into a single EQ-5D utility score ranging between -0.594 (representing severe problems) and 1 (representing no problem) by means of a standard regression model ((1), Appendix C). If response to one or more dimension is missing, the utility score will be missing.

Quality of life endpoints include response to each EQ-5D items over time and change in utility score over time during the OLE study from baseline of the parent study.

# 2.1.10 Health economic endpoints

Cost and detailed health resource utilization data will not be collected in this study. As a result, health economic endpoints, other than quality of life, will not be assessed.

#### 2.2 DISPOSITION OF PATIENTS

This section describes patient disposition for both patient study status and the patient analysis populations. Patient study status and the patient analysis populations will be presented overall as well as separately according to treatment (placebo versus alirocumab (regardless of dose)) received in the parent study.

Screened patients are defined as any patient who met the inclusion criteria and signed the informed consent form.

Enrolled patients consist of all screened patients with a treatment kit number allocated and recorded in the IVRS/IWRS database, regardless of whether treatment kit was used or not.

For patient study status, the total number of patients in each of the following categories will be presented in the clinical study report using a flowchart diagram or summary table:

- Screened patients
- Screen failure patients and reasons for screen failure
- Enrolled patients:
  - Enrolled but not treated patients and reason for not being treated;

- Enrolled and treated patients
- Patients who did not complete the open label study treatment period as per protocol
- Patients who discontinued the open label study treatment by main reason for permanent treatment discontinuation

For the last two categories of patients percentages will be calculated using the number of treated patients in the OLE as denominator.

The incidence of premature treatment discontinuation (irrespective of the reason) and premature treatment discontinuation due to AEs will be presented graphically during OLE study, using Kaplan-Meier method.

The proportion of patients with insufficient post-treatment follow-up among those who prematurely discontinued or completed the treatment will be described.

A patient having permanently stopped or completed the IMP is considered with insufficient post-treatment follow-up or without post-treatment follow-up at the end of the study in the following cases:

- If the patient has no post-treatment OLE follow-up call/visit, unless patient died before.
- If the post-treatment OLE follow-up call/visit is less than 9 weeks after the last IMP injection in OLE.

All major deviations potentially impacting efficacy analyses, enrollment and drug-dispensing irregularities, and other important deviations will be summarized in tables giving numbers and percentages of deviations. These deviations are listed in the data review and surveillance plan.

Additionally, the following populations will be summarized.

- Enrolled population
- Efficacy population: mITT population
- Safety population
- Anti-alirocumab antibody population
- Quality-of-life population

Definitions of the study populations are provided in Section 2.3.

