6.2 DURATION OF STUDY PARTICIPATION

6.2.1 Duration of study participation for each patient

The OLE study is planned to be completed in second quarter 2017 which corresponds to a study duration of approximately 168 weeks for the first patients enrolled or until the drug is commercially available for the patient in the respective country, whatever comes first. For patients in the UK, the study will last a maximum of 176 weeks.

The study duration includes up to approximately 3.5 years of treatment for the first patients enrolled, and 10 weeks of follow up after the last IMP injection for all the patients, those who will complete the study and those who will early discontinue whatever the reason.

The study will be considered as completed for a patient in the following situations:

- When the alirocumab is commercially available in the patient's country
- In second quarter 2017, if alirocumab is not yet commercially available in the patient's country

An EOT visit will be done 2 weeks after the last IMP injection and a safety follow up call 10 weeks after the last IMP injection.

The following situations will be considered as premature discontinuation of the patient from the study:

- Any withdrawal from the study to switch to an anti-PCSK9 inhibitor different from commercial alirocumab
- Any other reason

An unscheduled visit should take place within 5 days after the last IMP administration if possible, with assessments normally planned at the EOT visit, and a safety follow up call performed 10 weeks after the last IMP injection (see section 10.3.4).

The end of study per patient is the last protocol planned call. Patients with a Serious Adverse Events (SAEs) or an Adverse Event of Special Interest (AESI) should be followed until resolution, stabilization, or death.

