#### 1.2 OBJECTIVES

#### 1.2.1 Primary objective

The primary objective of this study is to assess the long-term safety of alirocumab when added to currently available lipid-modifying drug therapy, in patients diagnosed with heterozygous Familial Hypercholesterolemia who have completed one of the four parent studies.

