# 2.4.5.1 Analyses of adverse events

#### **Generalities**

The primary focus of AE reporting will be on TEAEs. Post-treatment AEs will be described separately.

If an AE date/time of onset (occurrence, worsening, or becoming serious) is incomplete, an imputation algorithm will be used to classify the AE as pre-treatment, treatment-emergent, or post-treatment. The algorithm for imputing date/time of onset will be conservative and will classify an AE as treatment-emergent unless there is definitive information to determine it is pre-treatment or post-treatment. Details on classification of AEs with missing or partial onset dates are provided in Section 2.5.1.

Adverse event incidence tables will present the number (n) and percentage (%) of patients experiencing an AE by SOC, HLGT (when applicable), HLT (when applicable), and PT. Multiple occurrences of the same event in the same patient will be counted only once in the tables within a treatment phase. The denominator for computation of percentages is the safety population.

Sorting within tables ensures the same presentation for the set of all AEs within the observation period (TEAE, and post-treatment). For that purpose, the table of all TEAEs presented by SOC and PT sorted by the internationally agreed SOC order and decreasing frequency of PTs within SOCs will define the presentation order for all other tables by SOC and PT, unless otherwise specified. The tables of AEs by SOC, HLGT, HLT and PT will be sorted by the SOC internationally agreed order and the other levels (HLGT, HLT, PT) will be presented in alphabetical order, unless otherwise specified.

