# Analysis of all treatment-emergent adverse event(s) leading to treatment discontinuation

• All TEAEs leading to treatment discontinuation, by primary SOC, HLGT, HLT, and PT.

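### The Kaplan-Meier curve for AE discontinuation in SAP 2.2 overstates cumulative incidence to the extent that patients stop for other reasons or die (minor)

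*SAP*

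**What the plan says.** SAP section 2.2 plans two curves. The sentence opens with "The incidence of premature treatment discontinuation (irrespective of the reason" and continues to the AE-specific curve: "premature treatment discontinuation due to AEs will be presented graphically during OLE study, using Kaplan-Meier method". No event definition, censoring rule or competing-risks method is given for either curve. The SAP does write censoring rules for its other Kaplan-Meier analyses (2.4.5.1 for selected TEAEs, 2.4.5.3 and 2.4.5.4 for PCSAs, 2.4.6 for low LDL-C), but none of them covers discontinuation.

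The same section also tabulates "Patients who discontinued the open label study treatment by main reason for permanent treatment discontinuation", and states that "percentages will be calculated using the number of treated patients in the OLE as denominator". In the safety section, the TEAE overview counts patients with a TEAE leading to permanent discontinuation, followed by a table of "All TEAEs leading to treatment discontinuation, by primary SOC, HLGT, HLT, and PT". For these AE tables, "The denominator for computation of percentages is the safety population".

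Protocol 6.2.1 separates two kinds of ending. Commercial availability in the patient's country, or reaching the second quarter of 2017, is completion. Premature discontinuation covers "Any withdrawal from the study to switch to an anti-PCSK9 inhibitor different from commercial alirocumab" and any other reason. Protocol 10.3.3 adds patient request, pregnancy or the intention of it, and sponsor request as grounds for stopping. Protocol 10.3.2 defines permanent discontinuation as a definitive decision not to re-expose the patient.

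**The concern.** A patient who has permanently stopped for a reason other than an AE, or who has died, can no longer stop because of an AE. For the AE curve these are competing events. Kaplan-Meier offers only event or censored, so under standard practice they are censored. Censoring assumes that such patients remain at the same later risk of AE discontinuation as those still on treatment; here that risk is zero.

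One minus Kaplan-Meier then describes the chance of stopping for an AE if nobody ever stopped for anything else. Even that reading requires the other stops to be unrelated to AE risk. The SAP sentence names a different quantity: the incidence among patients as they were actually treated.

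The stake is limited but real. The primary objective is long-term safety ("The primary objective of this study is to assess the long-term safety of alirocumab when added to currently available lipid-modifying drug therapy"), and treatment length varies with enrolment date and country launch, so crude percentages do not give the risk by a stated time. This curve is the only time-based estimate of overall AE discontinuation in the SAP.

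**Working it through.** **Inputs.** The documents state no AE-discontinuation rate, no dropout rate and no expected count, so there is no planned figure to reproduce. From the documents: a maximum treatment period of 168 weeks (SAP 1.1) and the split between completion and premature discontinuation (Protocol 6.2.1). Assumed: the true cumulative incidence by Week 168 of AE discontinuation, *a* = 3%, 5% or 10%; that of all competing stops, *o* = 5%, 10%, 20% or 30%; and constant cause-specific hazards.

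**Formulas.**
- Total cumulative hazard: H = −ln(1 − a − o)
- AE part: H_AE = H × a/(a + o)
- Value shown by one minus Kaplan-Meier when other stops are censored: 1 − exp(−H_AE)
- Value that a competing-risks estimator targets: a

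**Worked case, a = 5%, o = 20%.** H = −ln(0.75) = 0.2877. H_AE = 0.2877 × 0.05/0.25 = 0.0575. One minus Kaplan-Meier = 1 − exp(−0.0575) = 5.59%, against 5.00%: an excess of 0.59 points, or 12% relative.

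**One minus Kaplan-Meier at Week 168, all cases.**

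| True AE incidence | Other 5% | Other 10% | Other 20% | Other 30% |
|---|---|---|---|---|
| 3% | 3.08% | 3.16% | 3.35% | 3.58% |
| 5% | 5.13% | 5.27% | 5.59% | 5.97% |
| 10% | 10.27% | 10.56% | 11.21% | 11.99% |

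The excess runs from 0.08 points (3.08 − 3) to 1.99 points (11.99 − 10), or 2.6% to 19.9% relative. It depends mainly on *o*: about 3% relative when other stopping is 5%, and 19% to 20% when it is 30%.

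**Check with staggered completion.** In a simulation of 400,000 patients with the same hazards, administrative end was uniform between Weeks 60 and 168 (assumed) and results were read at Week 156.

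| Assumed at Week 168 | True incidence at Week 156 | 1 − Kaplan-Meier | Aalen-Johansen | Crude % |
|---|---|---|---|---|
| AE 5%, other 10% | 4.67% | 4.84% | 4.61% | 3.44% |
| AE 5%, other 20% | 4.69% | 5.16% | 4.65% | 3.50% |

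Aelen-Johansen recovers the true value to within simulation error, and Kaplan-Meier lies above it. The crude percentage is not pushed up by competing stops. It falls below the Week 156 incidence because many patients are followed for less than 156 weeks.

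**The case against.** The case for leaving the text alone is substantial. The curve is a graph in the disposition section of an uncontrolled, descriptive study, and no test, threshold or stopping rule uses it. The censoring of other-reason stops is the usual convention and not the SAP's wording. All the rates above are assumed, and some design features favour few other-reason stops: patients must have completed a parent study (Protocol 7.1), those with significant non-compliance are excluded (7.2.1), and commercial launch counts as completion (6.2.1). A cause-specific Kaplan-Meier curve is also a recognised net estimate, and labelling it as such would remove the misreading.

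Most of this stands, and it rules out three stronger readings that a reader might infer.
- **That a primary-objective figure is overstated.** The documents name no single primary statistic. The safety section reports AE discontinuation as crude n (%) of the safety population, which this mechanism does not inflate; nor does it inflate the percentages by reason in SAP 2.2.
- **That the published curves will fail to add up.** Only an all-reason and an AE curve are planned. They are nested, and no other-reason curve exists to be summed with the AE curve.
- **That the SAP prescribes the faulty censoring.** It is silent, and the point rests on standard practice.

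What does not stand is that the crude tables make the point moot. With unequal follow-up they answer a different question, as the simulation shows. A net label would be honest, but it would still not deliver the incidence that the sentence promises.

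**Conclusion.** The point holds as a minor method correction. If other-reason stops and deaths are censored, as is standard where no other rule is stated, the AE curve overstates the cumulative incidence of AE discontinuation. The direction is certain once any such stop precedes later AE discontinuations. The size is not known from the documents: about 0.1 to 2.0 percentage points for the assumed rates, 0.3 to 0.6 points for an AE incidence of 5% with 10% to 20% other stopping, and negligible if few patients stop for other reasons. The range rests on constant hazards and on rates chosen for illustration. Censoring at protocol-defined completion is legitimate, and the all-reason Kaplan-Meier curve is not affected by this problem.

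**What to change.** In SAP 2.2, replace Kaplan-Meier for AE discontinuation by a cumulative incidence function (Aalen-Johansen):
- **Event:** premature permanent discontinuation with an AE as main reason.
- **Competing events:** premature discontinuation for any other reason, and death not already counted as an AE discontinuation.
- **Censoring:** protocol-defined completion (commercial availability or second quarter 2017), and the cut-off date for ongoing patients in any interim analysis, in line with SAP section 3.

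Keep Kaplan-Meier for the all-reason curve and state its event and censoring rules in the same place. The crude tables need no change.

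The cost is one sentence in the SAP and a standard option in the planned SAS software. Reasons for stopping are already to be documented in the e-CRF (Protocol 10.3.3), so no new data are needed.
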